## **Protocol Change History**

Version	Description	Changed By
А	New	[name]
1.0	New	[name]

#### **List of Abbreviations**

ADE Adverse Device Effect

AE Adverse Event
AP Anteroposterior
BMI Body Mass Index

CFR Code of Federal Regulations

fCSM Functional Clinical Study Manager

eCRF Electronic Case Report Form

EDC Electronic Data Capture

EQ-5D EuroQol Five Dimensions Questionnaire

FDA Food and Drug Administration

GCP International Conference of Harmonisation Good Clinical Practice

HA Hydroxylapatite
HHS Harris Hip Score

HIPAA Health Insurance Portability and Accountability Act
ICMJE International Committee of Medical Journal Editors

IRB Institutional Review Board

ISO International Organization for Standardization

LEAS Lower Extremity Activity Scale

LRM Laser Rapid Manufacturing

PI Product Inquiry

PSF Particle Sintered Foam

QOL Quality of Life

ROM Range of Motion

SAE Serious Adverse Event

SC Study Coordinator VR-12 Veterans RAND-12

VICIZ VOLOTATIO TO TIAD 12

THA Total Hip Arthroplasty

UADE Unanticipated Adverse Device Effect

	Patient Consent Form.						
Diagnosis and Main	B. Patient is a male or non-pregnant female age 18-85 years of						
Inclusion/Exclusion	age at the time of study device implantation.						
Criteria*	C. Patient is a candidate for a revision of a failed acetabular						
	component with a cementless acetabular component.						
	D. Patient is willing and able to comply with postoperative						
	scheduled clinical and radiographic evaluations.						

#### **Exclusions**:

- E. Patient has a Body Mass Index (BMI) > 45.
- F. Patient is diagnosed with Inflammatory Arthritis.
- G. Patient has a non-Stryker retained stem.
- H. Patient has an active or suspected latent infection in or about the affected hip joint at time of study device implantation.
- Patient has a mental or neuromuscular disorder which would create an unacceptable risk of prosthesis instability, prosthesis fixation failure, or complications in postoperative care.
- J. Patient has compromised bone stock which cannot provide adequate support and/or fixation to the prosthesis.
- K. Patient is diagnosed with a systemic disease (e.g. Lupus Erythematosus) or a metabolic disorder (e.g. Paget's Disease) leading to progressive bone deterioration.
- Patient is immunologically suppressed or receiving steroids in excess of normal physiological requirements (e.g. > 30 days).
- M. Patient has a known sensitivity to device materials.
- N. Patient is a prisoner.
- \*Although this list is comprehensive from a clinical study patient selection perspective, the Investigator should always review the latest Instructions for Use (IFU) and Surgical Protocol prior to choosing subjects and performing surgery as newer versions may become available following study initiation.

# Diagnosis and Main Inclusion/Exclusion Criteria\*

	Required Components:							
	Trident II Tritanium Acetabular Shell:							
	o Clusterhole							
	○ Solidback							
	o Multihole							
	Trident II HA Hemispherical Clusterhole Shell							
	Trident II HA PSL Clusterhole Shell							
	Acetabular components must be used in a cementless							
	application.							
Study Device	If screws are used, only 6.5 mm Low Profile Hex Screws are permissible.							
	The following ancillary devices are permissible:							
	Compatible Stryker Modular Dual Mobility (MDM) acetabular							
	liner							
	Compatible Stryker X3 polyethylene inserts							
	Compatible Stryker femoral bearing heads							
	Compatible Stryker femoral stems							
	Hex Dome Hole Plug							
	Restoration Acetabular Wedge Augments							
Reference Therapy	Literature control, based on cementless acetabular revision.							
	Primary:							
	The 90% confidence interval of the success rate will be computed at							
	five years postoperative. For the non-inferiority comparison, the							
	lower bound of this 90% confidence interval will be compared with							
Statistical	90% survival rate. For the superiority comparison, the lower bound							
Methodology	of this 90% confidence interval will be compared with 95%.							
	Secondary:							
	Radiographic stability will be summarized in table format.							

#### **Evaluation Schedule**

Evaluation	Pre-op X-rays (-1 yr) eCRFs (-4 mos)	Intra op	6 week (+ 2 wks)	3-6 mos ( + 2wks)	1 year (+ 2 mos)	2 year ( + 2 mos)	3 year (+ 3 mos)	4 year (+ 4 mos)	5 year (+ 4 mos)	6 year (+ 4 mos)	7 year (+ 4 mos)	8 year (+ 4 mos)	9 year (+ 4 mos)	10 year (+ 4 mos)
Inclusion/ Exclusion	Х													
Demographics	Х													
Previous Implant Information		x												
Surgical Details		X												
HHS	X		Х		X	Х			X		Х			Х
Postoperative Events			Х		Х	X			Х		X			x
VR-12	Х		Х		Х	Х	Х	Х	Х		Х			Х
LEAS	Х		Х		Х	Х	Х	Х	Х		Х			Х
EQ-5D	Х		X		Х	Х	Х	Х	Х		Х			Х
Radiographs: Low AP Pelvis, Lateral	х		X	X	X	X			х		X			х
Follow-up Questionnaire*			X	Х	X	х	Х	X	X	X	X	X	X	Х

HHS: The HHS is an assessment that measures function, pain, deformity and motion.

VR-12: The VR-12 is a self-administered patient evaluation that evaluates general health and well-being.

Postoperative Events: The Postoperative Events form is a questionnaire completed by the Investigator intended to provide information on the patient's health status since the last follow-up visit.

LEAS: The LEAS is a self-administered patient evaluation designed to reflect patient activity.

EQ-5D: The EQ-5D is a standardized instrument for use as a measure of health outcome.

\*Follow-up Questionnaire: The Follow-up Questionnaire is a questionnaire intended to provide information on patient satisfaction, pain, and survivorship. \*Only administered when the patient is not present to complete the HHS.

Low AP Pelvis: Standard radiographic view of the pelvis containing bilateral hips and demonstrating the iliac bone, sacrum, pubis, ischium, femoral heads and necks, and greater or lesser trochanters.

Lateral: Standard radiographic view of the hip joint (can be the Lauenstein lateral, frog leg lateral or cross-table lateral) demonstrating complete visualization of the hip joint and femoral neck.

## 1 Introduction

This document is a protocol for a human research study. This study will be conducted in compliance with the protocol, Good Clinical Practice (GCP) Standards, associated Federal regulations and all applicable research requirements.

#### 1.1 Background

Total hip arthroplasty (THA) is one of the most clinically successful and cost-effective interventions in health care. The use of highly porous metals in cementless THA has yielded successful results at mid- to long-term follow-up. However, despite the improvements in implant designs and surgical techniques, there are cases in which the acetabular component is revised due to loosening, wear, or infection. Specifically, as reported in the literature, there is a 2% risk of revision for primary THA in the first 18 months after the index procedure and 1% thereafter in a 12-year study period.

Due to the expanding indications and aging population, the demand for THA is projected to increase by 174% by 2030, therefore triggering a subsequent rise in revision THA. During revision THA surgeons are confronted with greater technical and decision-making challenges due to the need to manage acetabular bone loss and poor quality of bone; all the while selecting proper implant and fixation strategy. As a result of these challenges, this can lead to compromised initial stability, which in turn leads to lack of long-term fixation and failure. However, with advances in cementless acetabular revision there have been improved results over the less than optimal cemented fixation.

In cases utilizing cementless acetabular components there is a required initial implant stability to allow for biologic fixation, which provides long-term durability of the prosthesis when properly achieved. To this end, there are several surface options available for cementless acetabular fixation; titanium fibermesh, sintered bead surfaces, plasma spray and trabecular metal are some widely used examples, all with good clinical history.

Particularly, the use of porous coated cementless cups in revision THA offers optimal biocompatibility therefore offering biological fixation. Delanois et al. published Kaplan Meier survivorship results on highly-porous titanium cups of patients who underwent revision THA,

reporting 97% survivorship at five years. Similar positive results have been reported at shorter time points for both porous-coated anatomic biologic fixation cups (6.6% loosening after 20 months) and titanium mesh ingrowth cups (1.4% failure after 41-month follow-up). Furthermore, Khatod et al. published revision femoral and acetabular rates of 39.43% (248 of 629 cases), and more specifically re-revision femoral and acetabular rates of 31.74% (20 of 63 cases) at five years.

Tritanium technology was developed to provide a three-dimensional Titanium matrix that resembles cancellous bone, allowing for enhanced acetabular fixation.

The Trident II Tritanium Acetabular Shell is a hemispherical acetabular shell indicated for cementless application. The Trident II HA Acetabular Shell is a hemispherical hydroxylapatite coated acetabular shell indicated for cementless application. Both shells are sterile, single-use devices indicated for use in revision total hip arthroplasty. The Trident II Clusterhole HA Acetabular Shells are available in both Hemispherical and Peripheral Self-Locking (PSL) outer geometry configurations and are compatible with all Trident polyethylene inserts, Trident Constrained Acetabular Inserts, and MDM liners. The Trident II Clusterhole HA Acetabular Shells are fabricated from forged Titanium (Ti-6Al-4V) ELI alloy per ASTM F136. The shells feature a coarse surface that provides initial fixation for cementless hip arthroplasty. The outer surface is coated with Commercially Pure (CP) Titanium followed by Hydroxylapatite powder (PureFix HA), which are each applied separately via a plasma spray process. The shell is subsequently machined to achieve the final product dimensions. The Trident II Tritanium Acetabular Shell and its predicate device, the Stryker Tritanium Acetabular Shell, have similar properties, with differences noted in material and manufacturing processes. The Trident II Tritanium Acetabular Shell is manufactured from Ti-6Al-4V via Laser Rapid Manufacturing (LRM) technology, as opposed to the Particle Sintered Foam (PSF) technology used to manufacture the Tritanium PSF Acetabular Shell coating from commercially pure titanium.

## 2 Clinical Study Plan

## 2.1 Study Design

A prospective, post-market, multi-center design will be employed. Radiographs will be assessed by an independent reviewer.

#### 2.2 Study Centers

#### 2.2.1 Centers for Data Collection

Cases will be enrolled at ten to fifteen centers. To allow for a learning curve with the use of the device, enrollment of cases into the study will commence when three cases have been completed at the center using the Trident II Acetabular Shell. The enrollment goal is a minimum of 25 cases per center utilizing the Trident II Acetabular Shell but will vary dependent upon the number of participating centers. Although a goal is presented, there is no maximum limit to the number of cases that a center may enroll. In the event that a center far exceeds the enrollment goal, Stryker may ask the center to cease enrollment so as not to skew the data. All participating centers will comply with the federal regulations regarding patient informed consent and Institutional Review Board (IRB) approval. Noncompliance of a study center may result in termination of the center's participation in the study.

#### 2.3 Number of Subjects

A minimum of 347 cases receiving the Trident II Tritanium or Trident II HA Acetabular Shell will be enrolled into the study.

# 3 Device Description

## 3.1 Study Device

The Trident II Tritanium Acetabular Shell is cleared for use in the United States under K161569 and K171768. The Trident II HA Shells have been cleared under K171768. See **Appendix A** for the FDA clearance letters.

The Trident II Tritanium Acetabular Shell is a hemispherical acetabular shell with a 3D engineered porous surface for biological fixation, made of Ti-6Al-4V alloy through additive manufacturing. The shell is built upon the design features and clinical history of the existing Tritanium Solid, Cluster, Multihole and Trident HA acetabular shells. Although they do have similar properties,

the material and manufacturing processes are different; the Trident II Tritanium hemispherical shell is manufactured from Ti-6Al-4V via Laser Rapid Manufacturing (LRM) technology, as opposed to the Particle Sintered Foam (PSF) technology used to manufacture the Tritanium PSF Acetabular Shell coating from commercially pure titanium. The Trident II HA Acetabular Shell is a hemispherical shell with hydroxylapatite coating and is indicated for cementless application. The Trident II HA Shells are an extension of the overall Trident System product line and feature the same insert locking mechanism as the current Trident product line. This advanced technology is designed to address the need for improved initial and biological fixation. The Trident II Tritanium Acetabular Shell, intended for use in a cementless application, is available in sizes from 42 mm through 72 mm and is compatible with Trident polyethylene liners, Mobile Dual Mobility (MDM) acetabular liners, and Trident II Tritanium acetabular screws. The Trident II HA Acetabular Shell is available in sizes 42 mm through 66 mm. Data in support of these marketing claims will be collected as part of the protocol.

The Trident II Tritanium and Trident II HA Acetabular Shell Product Labeling can be found in **Appendix B**.

The following acetabular component catalog numbers are permissible according to this study protocol and are in the following format, where 'XXY' varies by size:

The following bone screw catalog numbers are permissible according to this study protocol and are in the following format, where 'XX' varies by length:

The full listing of permissible acetabular component and bone screw catalog numbers may be found in **Appendix C**.

## 3.2 Ancillary Devices

Additionally, only the following **Stryker compatible** ancillary devices may be used, according to this study protocol:

- Compatible Stryker acetabular inserts
- Compatible Stryker MDM acetabular liner

- Compatible Stryker femoral bearing heads
- Compatible Stryker femoral stems
- Restoration Acetabular Wedge Augments
- o 6.5mm Low Profile Hex Screw
- o Hex Dome Hole Plug

The compatible Stryker acetabular inserts, acetabular liner, and heads are listed in the surgical protocol. All compatible ancillary devices will be used on-label only.

For reference, compatible Stryker femoral heads, acetabular liners and inserts are listed in **Tables 2-10** below. In the case of any uncertainty regarding device compatibility, the current versions of the Trident II Acetabular Shell surgical protocols should be reviewed.

Table 1: Trident II Tritanium Shell/Femoral Head/X3 Liner Compatibility

Solidback & Clusterhole *		42	44	46	48,50	52,54	56,58	60,62	64,66		
Multihole**		42	44	46	48,50	52,54	56,58	60,62	64,66	68,70	72
Liner Alpha Cod	le	Α	В	С	D	E	F	G	Н	1	J
Anatomic	44mm	-	-	-	-	-	3.8	5.4	7.1	8.6	10.6
Femoral	40mm	-	-	_	_	3.8	5.8	7.4	9.1	10.6	12.6
Heads	36mm	-	-	-	3.9	5.9	7.9	9.4	11.2	12.7	14.7
	32mm	-	3.9	4.9	5.9	7.9	9.9	11.4	13.2	14.7	16.7
Femoral	28mm	4.9	5.9	6.9	7.9	9.9	11.9	13.4	15.2	16.7	18.7
Heads	26mm	-	_	7.9	8.9	10.9	12.9	14.4	16.2	17.7	19.7
	22mm	7.8	8.8	9.8	10.8	12.8	14.8	16.3	18.1	19.6	21.6

\*Clusterhole shell sizes 42mm-50mm have 3-holes, and 52mm-66mm have 5-holes.

\*\*Multihole shell sizes 42-46mm have 8 holes, 48-50mm have 9 holes, 52-54mm have 11 holes, and 56-72mm have 13 holes.

Table 2: Trident II Tritanium Shell/Insert Compatibility

Alpha Code	Trident II Tritanium Shell Size (mm)	Trident 0°, 10° Inserts (mm)	Trident Eccentric 0°, 10° Inserts (mm)	Trident Elevated Rim Inserts (mm)
A	42	22, 28**	_	_
В	44	22, 28**, 32**	28*	-
C	46	22, 26, 28, 32**	28	28
D	48, 50	22, 26, 28, 32, 36**	28, 32	28
E	52, 54	22, 26, 28, 32, 36, 40**	28, 32, 36	28, 32, 36
F	56, 58	22, 26, 28, 32, 36, 40**, 44**	28, 32, 36	28, 32, 36
G	60, 62	22, 26, 28, 32, 36, 40**, 44**	28, 32, 36	28, 32, 36
H	64, 66	22, 26, 28, 32, 36, 40**, 44**	28, 32, 36	28, 32, 36
I	68, 70	22, 26, 28, 32, 36, 40**, 44**	28, 32, 36	28, 32, 36
J	72	22, 26, 28, 32, 36, 40**, 44**	28, 32, 36	28, 32, 36

Table 3: Trident II Tritanium Shell/MDM Liner/Insert Compatibility

#### Shell Size (mm), Liner Alpha Code

Trident II Tritanium Shell	46	48, 50	52, 54	56, 58	60, 62	64, 66	68,70	72
Liner Alpha Code	С	D	E	F	G	H	I	J
MDM CoCr Liner	36C	38D	42E	46F	48G	52H	5 4 I	58J
Poly Insert OD (mm)	36	38	42	46	48	52	54	58
Poly Insert ID (mm)	22.2	22.2	28	28	28	28	28	28
Nominal Poly Thickness (mm)	6.7	7.7	6.8	8.8	9.8	11.8	12.8	14.8

\*Available in  $0^{\circ}$  only. \*\* Available in X3 only and  $0^{\circ}$  only.

Table 4: Trident II PSL Clusterhole HA Femoral head, X3 Liner and Shell Compatibility

Shell size, liner alpha code, poly thickness and head size (mm)

Trident II PSL Clusterhole HA	\*	42	44	46	48, 50	52, 54	56, 58	60, 62	64, 66
Alpha code		A	В	C	D	E	F	G	H
Anatomic femoral heads	44mm	-	_	_	_	_	3.8	5.4	7.1
	40mm	_	_	_	_	3.8	5.8	7.4	9.1
	36mm	_	-	_	3.9	5.9	7.9	9.4	11.2
Femoral heads	32mm	_	3.9	4.9	5.9	7.9	9.9	11.4	13.2
	28mm	4.9	5.9	6.9	7.9	9.9	11.9	13.4	15.2
	22mm	7.8	8.8	9.8	10.8	12.8	14.8	16.3	18.1

\*Clusterhole shell sizes 42mm-50mm have 3-holes, and 52mm-66mm have 5-holes.

Table 5: Trident II PSL Clusterhole HA Shell

**Trident II PSL Clusterhole HA Shell** 

Alpha code	Trident II PSL Clusterhole HA Shell size (mm)	Trident 0°, 10° Inserts (mm)	Trident Eccentric 0°, 10° Inserts (mm)	Trident Elevated Rim Inserts (mm)	Trident 0° Constrained Inserts (mm)	Trident 10° Constrained Inserts (mm)
Α	42	22, 28**	_	_	_	_
В	44	22, 28**, 32**	28*	_	_	_
C	46	22, 28, 32**	28	28	_	_
D	48, 50	22, 28, 32, 36**	28, 32	28	22	_
E	52, 54	22, 28, 32, 36, 40**	28, 32, 36	28, 32, 36	22	22
F	56, 58	22, 28, 32, 36, 40**, 44**	28, 32, 36	28, 32, 36	28	22
G	60, 62	22, 28, 32, 36, 40**, 44**	28, 32, 36	28, 32, 36	28	28
Н	64, 66	22, 28, 32, 36, 40**, 44**	28, 32, 36	28, 32, 36	32	28

\*Available in 0° only

Table 6: Trident II PSL Clusterhole HA Shell MDM Liner and Insert Compatibility

#### Shell size (mm), liner alpha code

Trident II PSL Clusterhole HA Shell	46	48, 50	52, 54	56, 58	60, 62	64, 66
Alpha code	C	D	E	F	G	н
MDM CoCr Liner	36C	38D	42E	46F	48G	52H
Poly Insert OD (mm)	36	38	42	46	48	52
Poly Insert ID (mm)	22.2	22.2	28	28	28	28
Nominal poly thickness (mm)	6.7	7.7	6.8	8.8	9.8	11.8

\*\* Available in X3 only and 0° only

Table 7: Trident II Clusterhole HA: Femoral head, X3 Liner and Shell Compatibility

Shell size, liner alpha code, poly thickness and head size (mm)

Trident II Clusterhole H	A*	42	44	46	48, 50	52, 54	56, 58	60, 62	64, 66
Alpha code		A	В	C	D	E	F	G	H
Anatomic femoral heads	44mm	_	_	_	_	_	3.8	5.4	7.1
	40mm	_	_	_	_	3.8	5.8	7.4	9.1
	36mm	_	_	_	3.9	5.9	7.9	9.4	11.2
Femoral heads	32mm	_	3.9	4.9	5.9	7.9	9.9	11.4	13.2
	28mm	4.9	5.9	6.9	7.9	9.9	11.9	13.4	15.2
	22mm	7.8	8.8	9.8	10.8	12.8	14.8	16.3	18.1

\*Clusterhole shell sizes 42mm-50mm have 3-holes, and 52mm-66mm have 5-holes.

Table 8: Trident II Clusterhole HA Shell

**Trident II Clusterhole HA Shell** 

Alpha code	Trident II Clusterhole HA Shell size (mm)	Trident 0°, 10° Inserts (mm)	Trident Eccentric 0°, 10° Inserts (mm)	Trident Elevated Rim Inserts (mm)	Trident 0° Constrained Inserts (mm)	Trident 10° Constrained Inserts (mm)
A	42	22, 28**	_	_	_	_
В	44	22, 28**, 32**	28*	_	_	_
C	46	22, 28, 32**	28	28	_	_
D	48, 50	22, 28, 32, 36**	28, 32	28	22	_
E	52, 54	22, 28, 32, 36, 40**	28, 32, 36	28, 32, 36	22	22
F	56, 58	22, 28, 32, 36, 40**, 44**	28, 32, 36	28, 32, 36	28	22
G	60, 62	22, 28, 32, 36, 40**, 44**	28, 32, 36	28, 32, 36	28	28
H	64, 66	22, 28, 32, 36, 40**, 44**	28, 32, 36	28, 32, 36	32	28

\*Available in 0°only

Table 9: Trident II Clusterhole HA: MDM Liner and Insert Compatibility

#### Shell size (mm), liner alpha code

Trident II Clusterhole HA Shell	46	48, 50	52, 54	56, 58	60, 62	64, 66
Alpha code	C	D	E	F	G	H
MDM CoCr Liner	36C	38D	42E	46F	48G	52H
Poly Insert OD (mm)	36	38	42	46	48	52
Poly Insert ID (mm)	22.2	22.2	28	28	28	28
Nominal poly thickness (mm)	6.7	7.7	6.8	8.8	9.8	11.8

\*\* Available in X3 only and 0° only

#### 3.3 Device Implantation

All cases included in the analysis will receive the Trident II Acetabular Shell, in a revision setting, using manual instrumentation with an on-label approach. Only cases using an on-label approach in a revision setting may be included in the analysis.

## **4 Study Procedures**

#### 4.1 Subject Recruitment and Screening

Patients will be recruited at the study centers during preoperative visits through normal referral patterns. Advertising for the study at each center will be at the discretion of the investigator. All handouts, brochures, advertisements, etc. must be approved by the IRB prior to the dissemination of any recruitment materials to potential subjects.

During the preoperative visit, patients that are possible candidates for this study will be screened to determine if they meet the inclusion/exclusion criteria. If the patient is a candidate, the investigator will propose participation in the study to the patient, according to GCP guidelines. Patients must sign an IRB approved Informed Patient Consent Form prior to participation in the study, as well as prior to any data collection.

#### 4.2 Patient Informed Consent and Guidelines

All patients for this study will be provided an Informed Patient Consent Form describing this study and providing sufficient information for them to make an informed decision about their participation. The Informed Patient Consent Form must contain all elements required by the FDA under 21 CFR Part 50, in addition to any other elements required by state, local and institutional policies. See **Appendix D** for a copy of the applicable Model Informed Patient Consent. This will be submitted with the protocol for review and approval by each institution's overseeing IRB for the study. All patients must provide written consent after having had adequate time to consider their participation in the study. The formal consent of a patient, using the IRB approved Informed Patient Consent Form, must be obtained before that patient is submitted to any protocol related procedures that are not part of normal care. Written documentation of consent must be provided on the Informed Patient Consent Form's signature page in addition to a note in the patient medical records indicating the date that consent was obtained. The investigator-designated research professional obtaining the consent must also sign this Informed Patient Consent Form. The

patient or his/her legal representative should receive a signed copy of the Informed Patient Consent Form, according to GCP guidelines.

The procedure for obtaining informed consent is outlined below:

- Use a current IRB approved copy of the Informed Patient Consent Form.
- Review the Informed Patient Consent thoroughly with the patient before having them sign.
- After the patient has consented to the study procedures, ensure he/she signs and dates the Informed Patient Consent Form.
- The person obtaining consent also signs and dates the signature page.
- Provide a copy of the signed Informed Patient Consent Form to the patient.
- If required, provide the hospital with a copy of the signed Informed Patient Consent Form.
- Maintain the signed original in the patient's study chart.

## 4.3 Early Withdrawal or Termination of Subjects

#### When and How to Withdraw Subjects

In the event that a subject is discontinued by the investigative center prior to the final study evaluation, the subject will be notified by the center that he/she is no longer in the study and a Study Termination eCRF will be completed. If the reason for termination involves the study device not being implanted or surgery not performed, the subject will also be censored from analysis.

The following is a list of reasons for which subjects may be terminated from the study and the date of termination that should be used on the Study Termination eCRF in each situation. This list is not all inclusive:

Termination Reason	Date of Termination
Death	Date of death
Investigative center termination	Date of study close-out visit
Lost to follow-up	Date Stryker termination approval given
Voluntary withdrawal	Date subject notified center of withdrawal
Revision/removal of study device	Date of revision/removal procedure
Study device not implanted	Date of surgery
Surgery not performed	Date Stryker termination approval given

Revision or removal of the Trident II Acetabular Shell for any reason constitutes a failure and a study termination for the subject.

If revision of the femoral head, femoral stem, acetabular insert, or acetabular liner is required during the study, the event does not constitute a failure or study termination.

If the subject fails to return for his/her follow-up appointments, every effort should be made to contact the subject to assess his/her health status. If, after attempting to contact the subject through three documented phone calls and a certified letter, the subject still does not respond, he/she will be considered lost to follow-up. A Study Termination eCRF will be completed only after notifying Stryker of the subject's status and after Stryker has given approval to terminate.

In the event a subject does not have surgery, Stryker should be contacted to discuss if/when the surgery will be rescheduled. If the surgery is rescheduled more than 4 months from the date of consent, the subject will need to reaffirm participation in the study. All preoperative data will need to be recollected to be current within 4 months of study surgery. If the surgery is not to be rescheduled or if the subject is no longer considered an appropriate study candidate, a Study Termination eCRF may be completed only after notifying Stryker of the subject's status and after Stryker has given approval to terminate.

When a subject completes the study according to protocol at the final study evaluation, a Study Termination eCRF will be completed.

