#### 8 Statistical Plan

## 8.1 Study Objectives

## 8.1.1 Primary Objective Analysis

The primary hypothesis to be tested will be that the success rate at five years postoperative with the Trident II Acetabular Shell is not worse than 95% with a non-inferiority margin of 5%. That is, the following hypothesis will be tested:

H0: Pt <= 95% - 5% HA: Pt >95 % - 5%

Here, Pt is the success rate at five years postoperative with the Trident II Acetabular Shell. Case success at five years is defined as no incidence of revision and removal of Trident II Acetabular Shell for aseptic loosening within five years.

A 90% two-sided confidence interval will be computed for the success rate at five years. If the lower bound of the confidence interval is greater than a 90% survival rate, then the non-inferiority hypothesis will be supported, that is the five-year success rate is non-inferior to 95% with a margin of 5%. If the lower bound of the confidence interval is greater than 95% then it is supported that the five-year success rate is superior to 95%.

The Kaplan-Meier survival curve of revision and removal of the Trident II Acetabular Shell for aseptic loosening will be displayed using SAS/PROC LIFETEST.

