## 8.4.2 Sample Size Justification

Based on the literature review, it is reasonable to have a reference value of 95% of success rate at five years, and a case success at five years is defined as no incidence of revision and removal of Trident II Acetabular Shell for aseptic loosening within the five-year follow-up period. With the expectation that the success rate of Trident II Acetabular Shell for aseptic loosening within five years will be 94.5%, 277 cases will be needed to have a power of 95% to detect that the 5-year success rate is non-inferior to 95% with a margin of 5% at 5% significance level. After factoring a 20% lost to follow-up rate, a total of 347 cases will be needed.

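### Section 4.3 allows termination as lost to follow-up after one unanswered set of contact attempts, subject to sponsor approval, with no provision to check revision status at year 5

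*Combined protocol and SAP*

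**What the plan says.** Section 4.3 (When and How to Withdraw Subjects) starts from non-attendance: "If the subject fails to return for his/her follow-up appointments, every effort should be made to contact the subject". It then sets a stopping point: if after "three documented phone calls and a certified letter, the subject still does not respond, he/she will be considered lost to follow-up". The termination form may be completed only once the sponsor has been told and "after Stryker has given approval to terminate". The date entered for such a loss is "Date Stryker termination approval given". For a subject discontinued by the centre, "the subject will be notified by the center that he/she is no longer in the study and a Study Termination eCRF will be completed". Voluntary withdrawal is a separate row of the termination table.

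The rule is not tied to a number of missed visits or to the 5-year window. No section provides for later contact, re-entry or a year-5 status check, and none forbids them.

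Case success in section 8.1.1 is "no incidence of revision and removal of Trident II Acetabular Shell for aseptic loosening within five years". Section 8.4.4 restricts the primary efficacy analysis to subjects who can be evaluated at the 5-year endpoint, and section 8.3 imputes nothing. Section 8.4.2 allows for attrition: "After factoring a 20% lost to follow-up rate, a total of 347 cases will be needed". The Evaluation Schedule already has a questionnaire for patients who do not attend for the Harris Hip Score, "intended to provide information on patient satisfaction, pain, and survivorship".

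**The concern.** The retention rule suits scores that lose their meaning if not taken at the visit. The primary endpoint is different: whether the shell was revised for aseptic loosening within five years remains a fact that can be established later. A patient who could not be reached at year 1 or year 3 might answer at year 5, but the protocol gives the centre no duty to ask.

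Section 4.3 starts the loss, and sections 8.4.4 and 8.3 turn it into an exclusion from the primary analysis. Enrolling 347 instead of 277 protects precision, but it does nothing if the lost hips fail more often than the retained ones. A patient revised at another hospital and out of contact with the study centre is the obvious case, and missing such failures favours the device. With a fixed threshold and no concurrent arm, nothing offsets that bias. If the interval were taken from the Kaplan-Meier curve mentioned in section 8.1.1, informative censoring would raise the same problem.

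**Working it through.** **1. The plan's own figures.** Inputs from sections 8.1.1 and 8.4.2: threshold p0 = 0.95 − 0.05 = 0.90; expected success p1 = 0.945; one-sided 5% (lower limit of a 90% two-sided interval); power 95%; 20% loss.

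- n = p1(1 − p1)(1.645 + 1.645)² / (p1 − p0)² = 0.945 × 0.055 × 3.290² / 0.045² = 277.8 (stated: 277).
- 277 / 0.80 = 346.25, rounded up to 347 (as stated). The allowance is 347 − 277 = 70 hips.

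**2. Effect on power.** On the same formula, power = Φ(0.045√n / √(0.945 × 0.055) − 1.645).

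- n = 277: 95.0%.
- n = 312 (half of the 70 recovered): 96.7%.
- n = 260 (25% loss): 93.8%.
- n = 242 (30% loss): 92.3%.

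Power is not the main issue.

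**3. How loss can build up before year 5.** There are seven planned contacts through year 5: 6 weeks, 3-6 months, and years 1 to 5. Assume, for illustration only, the same independent chance q of an unanswered round at each contact, with every such round ending in termination. Cumulative loss is then 1 − (1 − q)⁷: 6.8% at q = 1%, 13.2% at 2%, 19.2% at 3% and 30.2% at 5%. If only the year-5 round counted, loss from this cause would be q itself. The documents give no value for q.

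**4. Effect on the false-positive rate.** Assumptions, none of them from the documents:

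- true overall failure is 10% (the null);
- the interval is an exact binomial one (section 8.1.1 names no method);
- 20% are lost, and lost hips fail at R times the retained rate;
- recovered hips are a random sample of the 70.

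Retained failure f solves 0.8f + 0.2Rf = 0.10, so f = 0.10 / (0.8 + 0.2R). Non-inferiority is declared with at most 19 failures in 277, 20 in 291, 21 in 300, or 22 in 312. The probability comes from the sum of Binomial(277, f) and Binomial(m, Rf), where m is the number recovered.

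| R | Retained / lost failure | m = 0 | m = 14 (20%) | m = 23 (33%) | m = 35 (50%) |
|---|---|---|---|---|---|
| 1 | 10.0% / 10.0% | 4.5% | 4.1% | 4.6% | 4.5% |
| 1.5 | 9.1% / 13.6% | 11.5% | 8.8% | 8.5% | 7.1% |
| 2 | 8.3% / 16.7% | 22.1% | 15.3% | 13.5% | 10.1% |
| 3 | 7.1% / 21.4% | 48.7% | 31.6% | 25.3% | 16.6% |

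Under these assumptions the reductions are upper bounds, because all 70 are treated as open to a second round. Subjects first lost in the year-5 window have already had that round, and deaths and withdrawals are not recoverable.

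**The case against.** A reader might infer that one missed visit ends participation automatically and for good, and that such subjects are never asked again at year 5. The text does not go that far. The trigger refers to appointments in the plural, the centre is told to try hard to reach the subject, and termination needs sponsor approval, which the sponsor could withhold until year 5 under the present wording. Permanence is inferred from silence. These points stand and limit the claim. They do not close the gap: approval has no stated criteria, the contact effort has a defined end, and a protocol that is silent on later contact obliges nobody to attempt it.

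Attrition is also partly addressed, by the 20% inflation, the remote questionnaire, and the reimbursement and stipend provisions of section 13.3. These limit loss but do not correct informative loss.

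The remedy has limits too. Nothing shown establishes that the questionnaire records the cause of a revision (its form specifications, Appendix G, are not available here), and the centre's chart may not show surgery done elsewhere. Recovering a usable endpoint may therefore need outside records. Patients who have been revised may also remain harder to reach, which would shrink the benefit below the random-recovery figures.

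Finally, the 10% failure rate is the null, whereas the plan expects 5.5%. That is the right setting for a type I error calculation, but it is not a forecast for this study.

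**Conclusion.** The point holds as a gap in the plan. Section 4.3 permits termination of a non-responder before year 5 after one unanswered set of attempts, with sponsor approval, and provides no year-5 status check. Sections 8.4.4 and 8.3 then remove that subject from the primary analysis.

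The size depends on whether loss is informative, and the documents are silent on that. If lost hips fail at 1.5, 2 or 3 times the retained rate, recovering 20-50% of them lowers false non-inferiority at most from 11% to 9-7%, from 22% to 15-10%, or from 49% to 32-17%. If loss is unrelated to outcome, the error stays at 4-5% and the gain is a small one in precision. It would be tempting to call these losses avoidable, but the documents do not show what share could be recovered. The case for change is that the step is cheap and can only reduce a possible bias in the device's favour.

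**What to change.** Amend section 4.3 as follows.

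- Do not complete the Study Termination eCRF for loss to follow-up before the 5-year window closes. Until then, record the subject as *visit missed, unreachable*.
- In the 5-year window, repeat the existing sequence of calls and certified letter using the Follow-up Questionnaire, and check the centre's chart for shell revision.
- If a revision is reported, request the operative record, where consent allows, to establish whether it was for aseptic loosening.
- Terminate as lost only if this also fails. Do not contact subjects who have withdrawn.

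The cost is a wording change, coordinator time for at most about 70 subjects (70/15 to 70/10, or roughly 5 to 7 per centre), some record requests, and records that stay open longer.
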